6.5.1 Rescue Medications

Protocol specific analgesic rescue medication for endometriosis-associated pain will include four equivalent NSAID choices and three equivalent opioid choices. The protocol-allowed analgesic rescue medications for endometriosis-associated pain are presented in Table 6–3. Investigators will prescribe a specific analgesic rescue medication for subjects at the time of Visit 2, taking into consideration the subject's preference and/or historical use of analgesics and the investigator's clinical judgement (based on the approved options).

Investigators are not to suggest or advise subjects on any modifications to their rescue medication regimen. Subjects will be instructed to contact the site if a change in their rescue analgesic medication is needed, such that appropriate adjustments can be considered. Investigators may then prescribe a different analgesic rescue medication (from each medication class if necessary) for the subject. Investigators should not prescribe more than one analgesic rescue medication from the same medication class at one time. The dosage outlined in Table 6-3 could be utilized, but all prescribed use of rescue analgesic medication should be according to appropriate clinical practice standards and the investigator's clinical judgment.

It is the investigator's discretion whether to withdraw a subject due to an analgesic issue.

Prophylactic use of protocol-specific rescue analgesic medications is not allowed. Use of any other analgesic medications for endometriosis-associated pain, including prophylactically, is not allowed from Visit 2 through the Follow-up Period.

Daily use of rescue analgesic medications taken for endometriosis-associated pain will be recorded by the subject in the e-Diary from Visit 2 through the Follow-up period including date of rescue medication use as well as the name, dosage and total number of the rescue medication within a 24-hour period. Detailed information on the rescue medication that will be sourced and provided to the subject can be found in the site operation manual. In addition, any pain medication taken for pain other than for rescue (such as treatment for toothache etc.) will be recorded in eCRF, not in the e-Diary.

Use of a prohibited medication for treatment of endometriosis-associated pain will be documented in the eCRF. If a subject continues to take analgesic(s) other than the protocol-

Version 6.0 42 of 138 April 11, 2024

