The use of rescue medication will be taken into account in the analysis of the primary endpoints. In the ANCOVA analysis, if a subject has at least 15% increase of rescue medication use (in terms of medication counts) compared to baseline in the EOT menstrual cycle, the measurement for Week 12 will be imputed with the baseline NRS measurement (i.e. assuming no improvement from baseline). In the MMRM analysis, if a subject has at least 15% increase of rescue medication use at a particular visit compared to baseline, the measurement at that visit will be imputed with the baseline NRS measurement. Such subjects will also be considered non-responders in the PGIC responder analysis for that visit. The visit window for the MMRM analysis will be defined in the SAP.

In addition to rescue medications, all analgesic medications taken to treat pain other than endometriosis-associated pain will be captured as concomitant medications. The pain intensity NRS measurement for endometriosis-associated pain in the days when these concomitant pain medications are used will be considered unevaluable and will be imputed by the corresponding average baseline measurement (i.e. assuming no improvement from baseline on those days).

To study the dose-response relationship, the CFB to Week 12 will be plotted versus dose. A simple linear regression model will be fitted as a function of dose to characterize the dose-response relationship. In case of lack-of-fit of the simple linear regression model, multivariate or non-linear regression models may be explored.

Version 6.0 65 of 138 April 11, 2024

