1. INTRODUCTION

HMI-115 is a highly specific human monoclonal antibody that will be investigated for safety and efficacy in pre-menopausal women with moderate to severe endometriosis associated pain.

A First in-human (FiH) study with HMI-115 has already established the safety and tolerability of HMI-115 when administered subcutaneously in post-menopausal women aged between 45 to 65 years in single doses up to 240 mg and multiple doses up to 90 mg once every 2 weeks (Q2W) for 6 weeks. This study aims to evaluate the safety and efficacy of HMI-115 versus a placebo in pre-menopausal women aged 18 to 49 years diagnosed with moderate to severe endometriosis associated pain.

The analyses described in this Statistical Analysis Plan (SAP) are based upon the following study documents:

- Study Protocol Version 6.1 (19 Sep 2024)
- Electronic Case Report Form (eCRF), Version 6.0 (12 Dec 2023)

Data will be summarized and listed according to the SAP. The details will be reflected in the document of Table, Listing, and Figure Shells.

The planned analyses identified in this SAP may be included in clinical study reports (CSRs), regulatory submissions, or future manuscripts. Also, post hoc exploratory analyses not necessarily identified in this SAP may be performed to further examine study data. Any post hoc, or unplanned, exploratory analyses performed will be clearly identified as such in the final CSR.

In addition, the SAP V1.3_special version for research paper publication is generated for the requirement of research paper publication only. Compared to the SAP V1.3, the change is that the SAF will be same as the PAS for all safety analysis.

PROJECT OVERVIEW

[figure not shown]

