6. PRIOR AND CONCOMITANT MEDICATIONS

Medications/procedures that start and stop prior to the date of first dose of IMP will be classified as Prior (P) only. If a medication/procedure starts before the date of first dose of IMP and stops on or after the date of first dose of IMP, then the medication/procedure will be classified as both Prior and Concomitant (PC). Medications will be classified as Concomitant (C) only if they have a start date on or after the date of first dose of IMP.

If medication/procedure start and/or stop dates are missing or partial, the dates will be compared as far as possible with the date of first dose of IMP. Medications/procedures will be assumed to be Concomitant only, unless there is clear evidence (through comparison of partial dates) to suggest that the medication/procedure started prior to the first dose of study medication. If there is clear evidence to suggest that the medication/procedure started prior to the first dose of IMP, the medication/procedure will be assumed to be both Prior and Concomitant, unless there is clear evidence to suggest that the medication/procedure stopped prior to the first dose of IMP. If there is clear evidence to suggest that the medication/procedure stopped prior to the first dose of IMP, the medication/procedure will be assumed to be Prior only.

Prior and concomitant medications will be coded according to the World Health Organization Drug Dictionary (WHO-DD) SEP2021 B3 or a later version.

Number and percentage of subjects with prior or concomitant medications will be summarized separately by anatomical therapeutic chemical (ATC) level 3, preferred name (PN) treatment group and overall using PAS. Summaries will be ordered alphabetically for ATC3, and then PN within ATC3.

Prior and concomitant procedures will be coded using the MedDRA 24.0 or a later version. Summaries of prior or concomitant procedures will be ordered alphabetically for SOC, and then PT within SOC.

Summary tables on prior medications/procedures will include "P" only, summary tables on concomitant medications/procedures will include "C" and "PC".

By-subject listings of medications and procedures will be provided, respectively.

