- The Week 12 measurement: Because the Week 12 (EOT) visit may or may not occur during menstruation, the measurement of Week 12 will be defined by the following 2 approaches, depending on the scenarios. The objective of these approaches is to capture a complete menstrual cycle (menstruation period should be ≥ 2 days) and designate it as the EOT menstrual cycle.

[figure not shown]
- If EOT visit occurs during menstruation, the EOT menstrual cycle is defined as the interval that begins from the first day after the end of the previous menstruation to the last day of the menstruation during which the EOT visit occurred. It is expected that the end of this menstruation may be days after the EOT visit.

- If EOT visit occurs outside of a menstruation period, the closest menstruation period to the EOT visit will be identified. This menstrual period may be before or after the EOT visit. In either case, the EOT menstrual cycle will begin at the end of the menstruation period immediately before the closest menstruation period to the last day of the closest menstruation period.

Or

The average score is calculated by adding up the daily DYS measured by NRS during analysis window and dividing by the actual number of days with non-missing daily DYS data.

The **primary estimand** is described by the following attributes:

Treatment conditions of interest:	HMI-115 at 60,120 and 240 mg vs. placebo. Placebo treatment is the control group.
Subject population:	Women with moderate to severe endometriosis-associated pain and have surgical diagnosis
Endpoint:	Mean change (change from baseline) in DYS measured by NRS at Week 12 measurement
Population-level summary:	Differences between each HMI-115 treatment group compared with placebo in mean change (change from baseline) in DYS measured by NRS at Week 12, including least square mean (LSM) with its associated standard error (SE) and 95% CIs by using ANCOVA
Intercurrent events (ICEs) and strategies to handle ICEs:	
Premature withdrawal from study treatment due to any reasons (Hypothetical strategy)
 
At least 15% increase in average pill count of rescue analgesic medications(endometriosis-associated) compared to Baseline. (Composite strategy)

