10. CHANGES TO THE PLANNED ANALYSIS

Surgically diagnosed subjects are this study's target subjects, and it complies with the request of the FDA and the global protocol to include subjects with surgical diagnosis only in the primary analysis, so the primary analysis population is changed from the FAS (subjects with randomized and taking at least one dose of IMP) to the subjects who have surgical diagnosis in the FAS. Subjects population with non-surgical diagnoses will be used as supplementary analysis. Compared to the Protocol version 6.1, the below corresponding updates have been done in the SAP version 1.3:

- 1) The primary objective is updated to study the efficacy of HMI-115 for 12 weeks compared with placebo in the management of endometriosis-associated pain based on subjects with surgical diagnosis.
- 2) A new analysis set - PAS is added in Section 3.3, which will be the primary analysis set for all efficacy analyses instead of FAS. While FAS will NOT be the primary analysis set. In addition, PPS will be a subset of the PAS instead of FAS. Both FAS and PPS will be the supplement for partial efficacy analyses.
- 3) For the subgroup analysis as defined in Section 7.1.6, the subgroup – “Surgical diagnosis vs. Non-surgical diagnosis” is removed.
- 4) The TFL Shells are updated accordingly following the SAP V1.3.

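### The protocol replaces pain scores on days with analgesics taken for other pain; the SAP averages those scores as recorded, so the two texts derive different primary endpoint values

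*Protocol*

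**What the plan says.** **Protocol 6.0.** Section 9.4.4 states that "all analgesic medications taken to treat pain other than endometriosis-associated pain will be captured as concomitant medications". NRS scores on the days of such use "will be considered unevaluable and will be imputed by the corresponding average baseline measurement", which the protocol explains as assuming no improvement on those days. Section 6.5.1 adds that this use "will be recorded in eCRF, not in the e-Diary". The revision history (Version 3.0 to 3.1) shows that the paragraph was added to answer an FDA comment on how such use would be handled in the efficacy analysis. It remains in the current text.

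**SAP.** Section 7.2.1 obtains the cycle average by summing the daily dysmenorrhea scores and "dividing by the actual number of days with non-missing daily DYS data". The only analgesic intercurrent event in its primary estimand is "At least 15% increase in average pill count of rescue analgesic medications(endometriosis-associated) compared to Baseline". Table 7.1, the pill count and Step 1 of Section 7.2.2 likewise concern rescue medication only. For other medications, Section 6 says: "Number and percentage of subjects with prior or concomitant medications will be summarized separately". They are also listed by subject, but nothing links them to the pain scores. Section 10 introduces its list of changes with "the below corresponding updates have been done in the SAP version 1.3". Its four items cover the objective, the analysis sets, a subgroup and the table shells.

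**The concern.** A score entered on a day when a tablet was taken for, say, toothache is a non-missing score. A programmer following the SAP averages it as recorded. A programmer following the protocol replaces it with the baseline mean. Because this use sits in the eCRF and not in the diary, the rescue pill count cannot pick it up. Without an explicit merge of medication dates with diary dates, the protocol rule will not be applied.

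At stake is the subject-level value of the primary endpoint. The protocol rule is worded for the NRS for endometriosis-associated pain in general, and SAP 7.3.2 and 7.3.3 reuse the same windows for non-menstrual pelvic pain and dyspareunia. Those secondary endpoints are therefore affected too. The rule was also a stated answer to a regulator, so its absence from the analysis document needs an explanation.

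**Working it through.** **Context figure.** Protocol 9.2 gives 80% power for a 1.4-point between-group difference with SD 2.0 and a two-sample t-test at 0.05. With 34 evaluable subjects per arm, two-sided, I obtain 81.2%. That figure is not in dispute; it only supplies a scale. The plan gives no figure for days with analgesics for other pain, so every frequency and score below is an assumption.

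**Subject level.** Let *B* be the baseline mean, *E* the daily score in the EOT menstruation (taken as the same on affected and unaffected days), *m* the number of scored menstrual days and *k* the number affected.

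- SAP change = *E* − *B*
- Protocol change = [(*m* − *k*)*E* + *kB*]/*m* − *B* = (*E* − *B*)(*m* − *k*)/*m*
- SAP minus protocol = (*k*/*m*)(*E* − *B*)

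| *B* | *E* | *m* | *k* | SAP change | Protocol change | Gap (absolute) |
|---|---|---|---|---|---|---|
| 7 | 4 | 5 | 1 | −3.0 | (4×4 + 7)/5 − 7 = −2.4 | 0.6 |
| 7 | 4 | 5 | 2 | −3.0 | (3×4 + 2×7)/5 − 7 = −1.8 | 1.2 |
| 6 | 4.6 | 5 | 1 | −1.4 | (4×4.6 + 6)/5 − 6 = −1.12 | 0.28 |

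For a 3-point improvement and one affected day, the gap runs from 3/3 = 1.0 in a three-day menstruation to 3/7 = 0.43 in a seven-day one. It is zero if no affected day falls in the window or if the affected score equals *B*. It is also zero for an improving subject whose change is already set to zero by the rescue-medication rule.

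**Arm contrast, unequal use.** Suppose both arms improve by 3 points, each affected subject has one affected day in five, and use differs by 10 percentage points. The contrast then differs between the two derivations by 0.10 × 0.6 = 0.06 points. That is 0.06/1.4 = 4% of the difference in Protocol 9.2 and 0.06/2.0 = 0.03 SD.

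**Arm contrast, equal use.** If a share *q* of every arm has a fraction *f* of menstrual days affected, the protocol rule shrinks a true difference of 1.4 to 1.4(1 − *qf*).

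- *q* = 5%, *f* = 20%: 1.4 × 0.99 = 1.386, power 80.4%
- *q* = 30%, *f* = 40%: 1.4 × 0.88 = 1.232, power 70.6%

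Power is for 34 per arm with SD held at 2.0. The second case is deliberately extreme. Equal use cancels in the contrast only if improvement is also equal. These figures measure the distance between two derivations, not an error in either.

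**Search for the rule elsewhere in the SAP.** Missing-data handling (7.1.3), the main approach (7.2.2), the sensitivity, supplementary and other analyses (7.2.3 to 7.2.5) and the secondary endpoints (7.3) contain no step for these days.

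**The case against.** Four points can be made on the other side.

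1. **Version.** The SAP is written against Protocol 6.1 of 19 September 2024, and only 6.0 was supplied. If 6.1 removed the rule, SAP Section 10 would have nothing to list. This stands as a caveat, although nothing supplied shows a removal.

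2. **Section 10.** A reader might infer from its silence that the rule was dropped without disclosure. The section does not support that much. It is framed around restricting the primary analysis to surgically diagnosed subjects and is not shown to be exhaustive. For example, the jump-to-reference imputation and the MMRM and LOCF sensitivity analyses of Protocol 9.4.3 do not appear in SAP 7.2.2 and 7.2.3, and Section 10 mentions neither change.

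3. **Handling elsewhere.** SAP 3.2 leaves action on affected data to a Protocol Deviation Specification that was not supplied. It may exclude these days. Exclusion would still differ from replacement by baseline.

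4. **Bias.** A reader might infer that the SAP counts analgesic-masked days as genuine relief, so that any imbalance in use biases the contrast. That would require every such analgesic to mask dysmenorrhea and the baseline mean to be the unbiased value. The documents establish neither. Neither estimand names this use as an intercurrent event, and the protocol rule itself discards a recorded score and assumes no improvement. The SAP nowhere calls these scores valid; it simply has no rule for them.

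Frequent use also cannot be presumed. Exclusion criterion 5 removes subjects with other chronic pain requiring chronic therapy that would interfere with assessment, and Protocol 6.5 restricts other pain medication. What remains after these points is the conflict between the two derivations.

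**Conclusion.** The point holds as a conflict between two stated derivations of the primary endpoint and of the NRS secondary endpoints. Read as written, Protocol 6.0 and the SAP give different values for a subject with an affected day whose score differs from her baseline mean. The size is (*k*/*m*)(*E* − *B*) per subject, or 0.6 points in the assumed example. The effect on the contrast is unknown because the documents give no frequency of such days. It is probably small, about 0.06 points under the assumed 10-point imbalance in use.

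Where treated subjects improve more and use is equal, the protocol rule is the more conservative of the two. It is a convention, not a proven unbiased value, so the documents do not support a finding that the SAP is biased. The conclusion is subject to two unseen documents, Protocol 6.1 and the Protocol Deviation Specification. It should be corrected before the analysis, but it does not undermine the design.

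**What to change.** In SAP 7.2.1, before averaging:

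- Match eCRF dates of analgesics taken for non-endometriosis pain to the calendar day that each diary entry describes. Protocol 8.1.3 has the subject rate the previous calendar day, so matching on the entry date would be one day out.
- Replace post-baseline NRS scores on matched days with the baseline-cycle mean, as the protocol states, for all three pain measures.
- For affected days in the baseline cycle, which the protocol leaves open and where replacement by the baseline mean is circular, set the score to missing and take the mean over unaffected days.
- State how partial or missing medication dates are mapped to diary days. SAP Section 6 uses them only to classify medications as prior or concomitant.

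If the rule was withdrawn on purpose, record that with a reason in SAP Section 10 and run the protocol rule as a sensitivity analysis. Either way, check Protocol 6.1 and the Protocol Deviation Specification for consistency.

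The cost is a few lines of SAP text and one merge of medication dates with diary dates. No new data are needed.

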9.4.5 Secondary Efficacy Endpoints

Efficacy

The analysis methods for the secondary endpoints are summarized in the table below. Details of model specifications and sample SAS codes will be presented in the SAP.

Measurement of Week 24: Because the Week 24 (EOS) visit may or may not occur during menstruation, the measurement of Week 24 will be defined by the following 2 approaches, depending on the scenarios. The objective of these approaches is to capture a complete menstrual cycle and designate it as the *EOS menstrual cycle*.

- If EOS visit occurs during menstruation, the *EOS menstrual cycle* is defined as the interval that begins from the first day of the previous menstruation to the day before the first day of the menstruation during which the EOS visit occurred.
- If EOS visit occurs outside of a menstruation period, the *latest* menstruation period prior to the EOS visit will be identified. The *EOS menstrual cycle* will begin at the end of the menstruation period *immediately before* the latest menstruation period to the end of the latest menstruation period.

Secondary Endpoints	Analysis Methods
Change of NMPP measured by NRS from	ANCOVA and MMRM methods as used for
Baseline to Week 12 and 24	the primary endpoint.
CFB in the monthly mean Endometriosis	ANCOVA and MMRM methods as used for
Daily Impact Pain Scale for DYS, NMPP and	the primary endpoint.
DYSP at Week 12 and 24	
Change of DYS measured by NRS from	ANCOVA and MMRM methods as used for
Baseline to Week 24	the primary endpoint.
Change of DYSP measured NRS from	ANCOVA and MMRM methods as used for
Baseline to Week 12 and 24	the primary endpoint.
CFB by visit in permitted rescue medication	The number of medication and the percentage
use	of days that permitted rescue medication is
	used will be summarized as two separate
	endpoints. Depending on the frequency of use

Version 6.0 66 of 138 April 11, 2024

Secondary Endpoints	Analysis Methods
	of permitted rescue medications, treatment comparison may be compared using an ANOVA with treatment and region as the main effects. The correlation between the use of rescue medications and the DYS and NMPP NRS will be explored by summary statistics and graphical presentations.
Change in menstrual period heaviness (bleeding) from Baseline by visit	The number and percentage of subjects in each category will be summarized by treatment group for baseline and each visit. Descriptive statistics for the percentage of days subjects had any uterine bleeding will be presented.

9.4.6 Handling of Missing Values

For the analyses using MMRM, missing data will not be imputed. Subjects with missing data will not be excluded from the MMRM analysis. The validity of the missing-at-random (MAR) assumption for the MMRM model will be assessed when interpreting the analysis results. For other analyses, the Last -Observation -Carried -Forward (LOCF) method will be used for post-baseline measurements. For subjects who prematurely discontinue before Week 12, the available observation corresponding to the last post-baseline visit will be carried forward to subsequent visits. Only the available observations in follow-up can be carried forward to Week 24.

9.4.7 Pooling of Investigator Centers

Data from all investigator sites will be pooled for analysis. The analyses will not be performed by center and will not include adjustment for centers.

